#### 2- Concise summary of project:

This trial will be a comparative effectiveness pragmatic multi-site randomized trial performed in singleton pregnancies with the diagnosis of PPROM between 24 weeks and 0 days - 32 weeks and 6 days. It will be comparing two well-accepted standardized treatments of care in this subject population: Erythromycin (FDA Category B) versus Azithromycin (FDA Category B). Our primary outcome will be the proportion of women still pregnant by day 7 after the diagnosis of PPROM is made. Our working hypothesis is that there is no measurable difference in the primary outcome between the group randomized to the azithromycin regimen versus the group randomized to the erythromycin regimen. Our secondary outcome will be latency defined as interval from PPROM to delivery. We propose a total of 324 subjects will be needed to complete the study.

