# 4- Study procedures:

Eligible subjects will be approached, and those who consent will be randomized to one of the two groups below in a 1-to-1 allocation.

- Erythromycin group: Ampicillin 2 gm IV every 6 hours first 2 days followed by amoxicillin 250 mg PO every 8 hours for next 5 days with erythromycin 250 mg IV every 6 hours for first 2 days followed by 500 mg PO every 8 hours for next 5 days (standard of care at UTMB).
- Azithromycin group: Ampicillin 2 gm IV every 6 hours first 2 days followed by amoxicillin 500 mg PO every 8 hours for next 5 days with azithromycin 1 gm PO once at randomization (Standard of care at UTMB).
   Both groups receive a total of 7 days of antibiotics as per standard of care at

The remaining standard of care will be the same for both groups concerning the management of PPROM according to NICHD/ACOG guidelines including GBS prophylaxis.

GBS chemoprophylaxis is beyond the scope of this trial, since we are randomizing the portion of macrolides only and not the Ampicillin portion that actually covers GBS. As noted, this regimen of intravenous ampicillin/ amoxicillin, is standard on both interventions and covers GBS. GBS cultures and GBS treatment is left per providers' discretion beyond our intervention period (7 days of latency antibiotics). In addition, drug adverse effects profiles between the two will be assessed in a post treatment subject survey. Subjects will complete a survey before being discharged from the hospital after receiving the assigned antibiotic regimen. Any questions will be answered and sufficient time will be given for the subject to fill the survey. Data will be collected retrospectively from EPIC EMR:

- Time of initiation of antibiotics to delivery.
- Maternal outcomes: chorioamnionitis, postpartum infectious morbidity, placental abruption
- Route of delivery

UTMB.

- Gestational age at delivery
- Adverse events: Allergic reactions (anaphylaxis, angioedema, skin rashes including Stevens Johnson and Toxic Epidermal necrolysis), GI symptoms (vomiting, diarrhea, constipation, ileus)
- Neonatal outcomes: perinatal death, need for oxygen supplementation (not intubated), ventilation support (intubated), necrotizing enterocolitis (NEC) stage 2 or 3, duration of ventilator support (intubated), NICU days and neonatal infection/sepsis, individually and as a composite.

Both survey forms and data forms are attached with protocol application.

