#### 3.6. Withdrawals

Subjects who withdraw from the study after randomization will be excluded from further follow-up. Outcomes ascertained up until the time of withdrawal will be reported in an intent to treat fashion. Those who withdraw prior to determining the primary outcome will be accounted for by randomizing an equal number of additional subjects.

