# 3.7 Outcomes

# Primary outcome:

• Proportion of undelivered subjects at day 7 from the diagnosis of PPROM

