# 12-Potential benefits:

In the background of erythromycin nationwide shortage, this will be the first level 1 trial to show that azithromycin may be equivalent to erythromycin in delaying delivery in patients with PPROM. This study may show for the first time that current alternative practice with azithromycin is as effective as erythromycin but with less adverse effects, less costly and easy administration.

13-**Statistical approach:** Analysis will be performed by intent to treat. Univariable analysis (such as t-test, Mann-Whitney or Chi-square) will be used for descriptive statistics such as patient demographics and assessment of primary outcome. Multivariable logistic analysis will be used to account for potential confounding variables. Sample size was calculated using a noninferiority trial design. Azithromycin will be tested against erythromycin for PPROM. The primary outcome will be the proportion of subjects undelivered

by day 7. For the sample size calculation, it is assumed the proportion undelivered in the erythromycin group would be 70% (pi = 0.7) based on Haas et al study. We considered that a difference in undelivered rate as large as 15% in favor of erythromycin would allow azithromycin to be non-inferior (delta = 0.15). This study will use 80% power to confirm non-inferiority and a one-sided confidence level of 97.5%.

Estimated sample size for two-sample comparison of proportions (non-inferiority)

Null hypothesis: p2 - p1 � delta (inferior), where:

pi (entered in command) is the overall proportion of participants expected to experience the outcome if the treatments are non-inferior, and delta is the smallest change in proportions between groups (p2 - p1) which would still be clinically important.

Alternative hypothesis: p2 - p1 < delta (non-inferior)

Note: a non-inferiority analysis is one-sided.

```
Assumptions:

power = 0.8000

alpha = 0.0250 (one-sided)

pi = 0.7000

delta = 0.1500

estimated required sample size (per group) = 147
```

The total estimated sample size is 294. Assuming 10% loss to follow, this study proposes a total of 324 subjects will be needed to complete the study. The STAT 14 (Dallas, Tx) will be used for statistical computations. This trial will be registered with Clinical Trials Register (Clinicaltrials.gov), before recruitment is initiated and after IRB approval."

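### The total of 324 allows for about 9% unreplaced loss, not the stated 10%; the shortfall is about 2 women and power falls only to 79.8%

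*Combined protocol and SAP*

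**What the plan says.** Section 13 (Statistical approach) sizes the trial for non-inferiority on the proportion of women undelivered at day 7. It assumes 70% undelivered, a margin of 0.15, 80% power and "alpha = 0.0250 (one-sided"). The printed output ends with "estimated required sample size (per group) = 147", and the text continues: "The total estimated sample size is 294". The next step is the allowance for loss: "Assuming 10% loss to follow, this study proposes a total of 324 subjects". No formula is given for going from 294 to 324.

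Two other places matter. Section 2 (Concise summary of project) repeats the total: "We propose a total of 324 subjects will be needed to complete the study". Section 3.6 (Withdrawals) has a replacement rule: "Those who withdraw prior to determining the primary outcome will be accounted for by randomizing an equal number of additional subjects". Neither section 3.6 nor section 13 says how that rule and the 10% allowance fit together.

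**The concern.** A loss rate is normally a fraction of the women randomized. On that reading, the number to randomize is the number required divided by the fraction retained, so that the required number is left after the loss. Here 324 with 10% lost leaves fewer than 294, so the total, the loss rate and the evaluable number do not agree when the lost women are not replaced.

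What is at stake is the internal consistency of the sample-size statement. That statement is usually carried into the trial report, where any reader can check it with one multiplication. The base calculation has almost no slack above 80% power, so even a small shortfall takes it just under the stated target. The conduct and interpretation of the trial are not at risk.

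**Working it through.** **Inputs.** From section 13: proportion undelivered 0.70 in both groups, margin 0.15, one-sided alpha 0.025, power 0.80, loss 10%, total 324. From section 4 (Study procedures): 1:1 allocation.

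**Step 1: reproduce the base figure.** With the usual normal approximation,

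n per group = (1.960 + 0.842)² x 2 x 0.70 x 0.30 / 0.15² = 146.5,

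which rounds up to 147 per group and 294 in total. Both match the plan. The unrounded total is 2 x 146.5 = 293.0.

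**Step 2: reproduce the inflated total.**

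- Adding 10%: 294 x 1.1 = 323.4, rounded up to 324. By group, 147 x 1.1 = 161.7, rounded up to 162, and 2 x 162 = 324. Both routes give the plan's figure.
- Dividing by the fraction retained: 294 / 0.9 = 326.7, rounded up to 327. By group, 147 / 0.9 = 163.3, rounded up to 164, and 2 x 164 = 328. Neither gives 324.

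**Step 3: what 324 leaves after 10% unreplaced loss.** 324 x 0.9 = 291.6 women, or 145.8 per group. That is 2.4 below 294 and 1.4 below the unrounded 293.0.

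**Step 4: the loss that 324 can absorb.** (324 - 294) / 324 = 30/324 = 9.3%. Against the unrounded requirement, (324 - 293.0) / 324 = 9.6%.

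**Step 5: power.** Power = Φ(0.15 x √(n / 0.42) - 1.960), where n is the number per group and 0.42 = 2 x 0.70 x 0.30.

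| Evaluable per group | Power |
|---|---|
| 147 (the plan's requirement) | 80.1% |
| 145.8 (324 with 10% unreplaced loss) | 79.8% |

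The difference is 0.3 percentage points from the rounded-up design and 0.2 points from the nominal 80%.

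**The case against.** The strongest objection is the replacement rule in section 3.6. If every lost woman withdrew before her primary outcome was known and was replaced, no evaluable women would be missing. A reader might infer from section 13 alone that the total, the loss rate and the power can never hold together. The documents do not support that, because the conflict needs unreplaced losses above about 9.3%. What remains is that section 3.6 covers withdrawal only. It does not mention other losses. For example, section 3.3 counts a woman in the intent-to-treat analysis only once the assigned antibiotics are dispensed, so a woman randomized but never dispensed could be missing without having withdrawn. And if replacement covered every loss, the 10% allowance would have no purpose.

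A second objection is that such losses should be few. The outcome is fixed at day 7, there are no follow-up visits (section 3.5), outcomes are assessed in hospital (section 3.4) and data come from the medical record (section 4). This is fair. It makes the shortfall less likely but does not reconcile the printed figures.

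A third is that the discrepancy is close to rounding: 9.6% rounds to 10%, and 79.8% rounds to 80%. This also stands as a statement about size. Still, 291.6 is below even the unrounded 293.0, so rounding of the base figure does not account for it.

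Finally, it is tempting to say that the plan multiplied by 1.1. No formula is printed, and the loss allowance can also be read as 10% added to the requirement. The exact match makes the multiplication likely, but it remains an inference. The shortfall in step 3 does not depend on it.

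**Conclusion.** The point holds as a minor inconsistency. On the plan's own inputs, 324 falls about 2 evaluable women short of 294 if 10% of those randomized are lost and not replaced, and power is then 79.8% instead of 80%. At unreplaced loss of about 9.3% or less, 324 is enough.

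This rests on two assumptions: that the 10% is a fraction of the women randomized, and that some losses fall outside the replacement rule in section 3.6. The documents do not settle either.

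A reader might go further and infer that the trial is underpowered or must enrol more women. The figures do not support that: a change of 0.2 to 0.3 percentage points in power is negligible, and the base calculation of 147 per group reproduces exactly.

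**What to change.** Keep 324 and correct the sentence in section 13 in one of two ways:

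- state that 324 allows for about 9% unreplaced loss (30/324 = 9.3%); or
- keep the 10% and state that power at 10% unreplaced loss is 79.8%.

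In the same sentence, say how the allowance relates to section 3.6: whether replacements are randomized on top of 324 or counted within it, and which losses the allowance is meant to cover. Section 2 can stay as it is, since the total does not change.

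The cost is a wording change, with no effect on design, analysis or recruitment. Raising the total to 328 (164 per group) would also reconcile the figures, but it means 4 more women and is not needed for a difference of this size.
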